Improvement of renal function (SCr) from Day 1 through end of treatment, repeated measure analysis. SCr will be collected at baseline and daily from Day 1 through end of treatment.

Secondary Efficacy Endpoints:

- Improvement of renal function (SCr) from Day 1 through end of treatment, repeated measure analysis as compared to the Retrospective Control Group.

Collaborative Research Study, Version 4: 06/29/21
To Treat HRS-AKI Patients with Continuous Terlipressin Infusion

- For the Prospective Terlipressin Group alone and also in comparison to the Retrospective Control Group:
 - Incidence of dialysis by Day 30 and Day 90 of follow up.
 - Survival by Day 30 and Day 90 follow up.
 - Transplant by Day 30 and Day 90 follow up.
 - Serum creatinine at Day 30 and Day 90 follow up
 - Serum creatinine and incidence of dialysis at Day 30, Day 90, Day 180, and Day 365 after liver transplantation
 - Incidence of kidney transplant within one year after liver transplant
 - Descriptive analysis of number of simultaneous liver kidney transplants and episodes of graft rejection by Day 90 and Day 365 after liver transplant

Safety:

Safety review and assessments will be made only for the Prospective Terlipressin Group and will include the following:

- Serious adverse events up to 30 days after end of treatment.

Statistical Methods:

A formal sample size calculation is not applicable for this study. It is expected that at least 50 subjects across more than 5-10 institutions may receive terlipressin treatment during the course of the research study.

Additionally, up to 150 subjects across all clinical sites will have their Retrospective data collected. Descriptive analysis will be planned for the efficacy and safety data collected. Sponsor may perform additional analysis not specified in study protocol.

Contents

1	SYNOPSIS	10
2	LIST OF ABBREVIATIONS	22
3	INTRODUCTION	24
3.1	HEPATORENAL SYNDROME	24
3.2	TERLIPRESSIN	25
3.3	EFFICACY	25
3.4	SAFETY	26
3.5	RETROSPECTIVE CONTROL GROUP: M&O TREATED SUBJECTS	26
3.5.1	MIDODRINE AND OCTREOTIDE	26
3.5.2	M&O OFF-LABEL USE	26
4	STUDY RATIONALE	27
5	SAFETY AND EFFICACY ASSESSMENTS	27
5.1	EFFICACY VARIABLES	27
6	INVESTIGATIONAL PLAN	28
6.1	OVERALL STUDY DESIGN AND PLAN: DESCRIPTION	28
7	STUDY POPULATION	29
7.1	POPULATION RATIONALE	29
7.2	NUMBER OF SUBJECTS TO BE STUDIED	29
7.3	INCLUSION/EXCLUSION CRITERIA	29
7.4	SUBJECT WITHDRAWAL CRITERIA	31
7.5	PROTOCOL DEVIATIONS	31

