5.1 Efficacy Variables

The efficacy variables are summarized below, and further details are provided in Section 13.

Primary Efficacy Assessment:

Improvement of renal function (SCr) from Day 1 through end of treatment, repeated measure analysis. SCr will be collected daily, from Day 1 through end of treatment. Baseline SCr will also be entered.

Secondary Efficacy Endpoints:

- Improvement of renal function (SCr) from Day 1 through end of treatment, repeated measure analysis as compared to the Retrospective Control Group.
- For the Prospective Terlipressin Group alone and also in comparison to the Retrospective Control Group:
 - Incidence of dialysis by Day 30 and Day 90 of follow up.

Collaborative Research Study, Version 4: 06/29/21
To Treat HRS-AKI Patients with Continuous Terlipressin Infusion

- Survival by Day 30 and Day 90 follow up.
- Transplant by Day 30 and Day 90 follow up.
- Serum creatinine at Day 30 and Day 90 follow up
- Serum creatinine and incidence of dialysis at Day 30, Day 90, Day 180, and Day 365 after liver transplantation and those alive without transplantation (transplant eligible and ineligible patients)
- Incidence of kidney transplant within one year after liver transplant.
- Descriptive analysis of number simultaneous liver kidney transplants and episodes of graft rejection at Day 90 and Day 365 after liver transplant.

Safety:

Safety review and assessments will be made only for the Prospective Terlipressin Group and will include the following:

- Serious adverse events up to 30 days after end of treatment.

6 Investigational Plan

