15.1 Primary Analysis

The primary analysis will utilize mixed effects regression modeling to estimate changes in serum creatinine (SCr) over the study period, accounting for baseline SCr and the correlation structure between the repeated measures. All potential confounders will be added to the model and sequentially removed if they do not confound the association between receipt of terlipressin and improvement in Scr. Those confounders resulting in a $\geq 10\%$ change in the coefficient for the association between terlipressin and improvement in SCr will be retained in the final model. For all generated models, Aikaike Information Criteria (AIC) scores will be calculated and compared. The model with the smallest absolute AIC value will be accepted as the most parsimonious and will be used as the primary model for the explanation of study results. As has been undertaken in other terlipressin studies in HRS, a least-squares means analysis will be conducted using a repeated-measures analysis of variance. The results from this approach to the statistical analysis can then be directly compared to prior study results.

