15.2 Secondary Analyses

A number of secondary outcomes will be examined for the study cohort. These outcomes include the incidence of dialysis, mortality, and liver transplantation at day 30 and 90. The

incidence of kidney transplant within one year of liver transplant will also be determined. Additionally, descriptive comparisons of SCr will be undertaken at day 30 and 90 of follow up and at 4 time points after receipt of liver transplantation (day 30, 90, 180 and 365) and also at similar time points for those patients who were transplant ineligible or did not undergo a transplant. Incidence will be calculated as the number of new events during the observation period divided by the total persons at risk. All statistical analyses will be conducted using Stata version 15.1 statistical software (StataCorp, College Park, TX). Statistical significance will be declared for a two-sided hypothesis test if the *P* value was <0.05.

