15.3 Sample Size Considerations

A formal sample size calculation is not applicable for the proposed study. However, at least 50 subjects across more than 5-10 institutions may receive terlipressin treatment during the course of the intervention portion of the study. For the comparison of the terlipressin treatment group and retrospective controls, we expect to have 50 subjects in the intervention group and 150 subjects, assembled from the study sites, in the control group. Assuming a type 1 error of 0.05 and power of 80%, we expect to be able to detect a range of differences in serum creatinine (SCr) depending on the standard deviation of the change (primary endpoint) expected for the groups (see below). Based on results from the REVERSE trial, a change in SCr of as small as 0.05 mg/dL would be able to be detected if the standard deviation for the change approximated 0.10 mg/dL and a pre-specified sample size of 200 subjects, 50 of whom are in the intervention arm, is used for the calculation.

	Δ SCr mg/dL				
Detectable Difference	0.46	0.34	0.23	0.11	0.05
Standard Deviation	1.00	0.75	0.50	0.20	0.10

Given the relatively small number of subjects proposed for inclusion in this terlipressin study, we will likely be underpowered to detect a difference in the other secondary outcomes being explored.

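### Section 15.1 picks the primary SCr model by smallest absolute AIC over all generated models, without tying that choice to its own 10% confounder rule

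*Combined protocol and SAP*

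**What the plan says.** Section 15.1 fits a mixed effects regression to SCr, adjusted for baseline SCr, and selects covariates by backward elimination: "All potential confounders will be added to the model and sequentially removed if they do not confound the association". Confounders producing a 10% or greater "change in the coefficient for the association between terlipressin and improvement in SCr will be retained in the final model". Two sentences on AIC follow directly: "For all generated models, Aikaike Information Criteria (AIC) scores will be calculated and compared", and "The model with the smallest absolute AIC value will be accepted as the most parsimonious and will be used as the primary model". A repeated-measures ANOVA with least-squares means is added so that results can be set beside earlier studies. The section does not list the candidate confounders, define which models count as generated, or limit AIC to any subset of them.

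Other sections bear on the status of this model. Section 5.1 lists as secondary the "repeated measure analysis as compared to the Retrospective Control Group", yet the model in 15.1 is built around a terlipressin coefficient, which needs the control group. Section 15.3 sizes that same comparison at 50 versus 150 subjects, "depending on the standard deviation of the change (primary endpoint) expected for the groups". The synopsis says "Descriptive analysis will be planned for the efficacy and safety data collected", but 15.2 says "Statistical significance will be declared for a two-sided hypothesis test if the" P value is below 0.05.

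**The concern.** The two rules answer different questions. The 10% rule asks whether a covariate moves the terlipressin coefficient. AIC asks whether it improves fit by more than the cost of one parameter. A covariate that is imbalanced between groups but weakly related to SCr can pass the first and fail the second. A strong predictor of SCr that is balanced between groups does the reverse.

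The controls are historical, so covariate adjustment is the main protection that Section 15 offers for the comparison. If the retention rule and the selection rule point to different covariate sets, an analyst who has seen the results could defend either as planned. The ANOVA does not remove the problem, because the label *primary* goes to the AIC choice.

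The word *absolute* is a second defect. AIC is ordered on its signed value, so ordering on magnitude reverses the ranking whenever the values are negative.

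**Working it through.** **1. What counts as generated.** The text allows two readings.

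- (a) Every model fitted during elimination counts, including those fitted only to test a covariate. AIC can then choose a model that lacks a retained confounder.
- (b) Only the accepted removal steps count. Every candidate then contains all retained confounders, so none is lost. AIC can still prefer an earlier, larger model holding covariates that the 10% rule removed.

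**2. When a retained confounder is lost under (a).** Dropping one covariate saves 2 AIC points, so AIC drops it when its likelihood-ratio chi-square is below 2. With one value per subject and n = 200, that means n x ln[1/(1 - r²)] < 2, so r² < 1 - exp(-2/200) = 0.00995 and r < 0.100. The covariate shifts the terlipressin coefficient by about imbalance x 0.100. It passes the 10% rule when this is at least 0.10 x effect. The conflict therefore needs an imbalance of about 0.46 SD at an effect of 0.46 SD, and about 1.00 SD at an effect of 1.0 SD.

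**3. Two worked mixed models** (assumed data; random intercept, maximum likelihood, 50 versus 150 subjects, 7 days, covariates c1 and c2). Each cell gives the terlipressin coefficient and the AIC.

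| Model | Between/within SD 0.9/0.5 | Between/within SD 0.09/0.05 |
|---|---|---|
| c1 + c2 | -0.4802; 2658.9 | -0.0147; -3785.8 |
| c2 only | -0.4200; 2662.6 | -0.0112; -3786.6 |
| c1 only | -0.5323; 2711.3 | -0.0206; -3730.7 |
| neither | -0.4620; 2715.3 | -0.0124; -3727.3 |

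- First data set: dropping c1 changes the coefficient by (0.4802 - 0.4200)/0.4802 = 12.5%, and dropping c2 by (0.5323 - 0.4802)/0.4802 = 10.8%. The 10% rule keeps both. Lowest AIC also picks the full model, so the rules agree.
- Second data set: the changes are (0.0147 - 0.0112)/0.0147 = 24% and (0.0206 - 0.0147)/0.0147 = 40%. The 10% rule again keeps both. Under reading (a), lowest signed AIC picks c2 only, by 0.8 points. Smallest absolute AIC among the three models that elimination would fit picks c1 only, which is 3785.8 - 3730.7 = 55.1 points worse than the full model. If the model with neither were also fitted, the literal rule would pick that one.

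**4. Can AIC be negative in this trial?** For a given total residual SD s, the Gaussian -2 log-likelihood at its maximum is at most ln(2π) + 1 + ln(s²) per observation, whatever the within-subject correlation. That bound is below zero when s < exp[-(1.838 + 1)/2] = 0.242.

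- s = 0.20: 2.838 - 3.219 = -0.381 per observation.
- s = 0.10: 2.838 - 4.605 = -1.767 per observation.

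With 200 subjects and at least three days each (600 observations), the s = 0.20 bound is 600 x -0.381 = -229. The 2-points-per-parameter penalty for a model of this size does not bring that back to zero. For larger total SDs the sign depends on the within-subject part: AIC turns negative only below about 0.139 mg/dL (5 days, between-subject SD 1.0) to 0.221 mg/dL (14 days, between-subject SD 0.2). The SDs in 15.3 describe per-subject change, so carrying them over to the model residual is an assumption.

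**5. How often the rules disagree, and at what cost.** The effect scale comes from 15.3. Reproducing its first row: (1.960 + 0.842) x 1.00 x sqrt(1/150 + 1/50) = 0.458, stated as 0.46. The stated rows equal 0.46, 0.45, 0.46, 0.55 and 0.50 SD. Assumed for the simulation: eight candidate covariates biasing in mixed directions, imbalance 0.3 or 0.5 SD, coefficients 0.05-0.20 SD, treatment lengths of 3-14 days, random-intercept maximum likelihood, and 1000 runs per setting.

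| Effect (SD) | (a): retained confounder dropped | (a): opposite P<0.05 verdict |
|---|---|---|
| 0.46 | 7-47% | 2.9-5.9% |
| 0.55 | 4-29% | 1-4% |
| 0.7 | 2-12% | about 1% or less |
| 1.0 | 0-2% | none |

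Under (b) at 0.46 SD, AIC keeps a larger model in 30-90% of runs and the verdict differs in 0.7-3.5%. Mean bias under the two rules differs by 0.007 SD or less. When a confounder is dropped, the coefficient moves by a median 0.03-0.05 SD, against an unadjusted standard error of sqrt(1/50 + 1/150) = 0.163 SD. In a simpler least-squares version at 0.46 SD, drops fell from 21-46% at coefficient 0.10 to about 1% at 0.30.

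**The case against.** The best reply has four parts.

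- **The plan does rank the rules.** It gives the word *primary* to the AIC choice. A reader might infer that 15.1 leaves the two rules wholly unranked, and the text does not support that. What stands is narrower: a retention rule that the selection rule may override, with no statement of which models AIC ranges over.
- **AIC may have been meant only for the correlation structure, or only among models passing the 10% rule.** That would be coherent, but 15.1 says neither, and the reference to all generated models comes straight after the covariate-removal sentences.
- **The harm is small.** The 0.46 SD is a detectable difference, not an expected effect. Section 3.5.2 cites HRS reversal of 55.5% versus 4.8% for terlipressin against M&O. On a probit scale that is 0.14 + 1.66 = 1.80 SD, where drops and verdict changes were zero in a least-squares rerun. This is only a rough guide: reversal is not SCr change, and controls here may have had other vasopressors. In the other direction, some assumed covariate sets at 0.46 SD gave verdict changes of 8%, or about 10% with all biases in one direction. A reader might take the drop rates of up to 47% as a forecast for this trial. They describe weak assumed confounders, and strong predictors are not lost.
- **The comparison is listed as secondary and called descriptive.** That is so, but 15.2 attaches a significance verdict and 15.3 sizes this comparison.

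A reader might also infer that the absolute-value wording will certainly reverse the ranking. The documents do not show this, because the SD rows run up to 1.00 mg/dL.

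**Conclusion.** The concern holds as a conflict between two stated rules in 15.1. The AIC choice can omit a weak confounder that the plan says is retained (reading a) or keep covariates that it says are removed (reading b). No other section reconciles them. Separately, ranking on absolute AIC is wrong whenever AIC is negative, which follows if the residual SD is near the two smallest rows of the 15.3 table.

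The conflict needs no simulation, but its size does, and the size rests on assumed covariates, imbalances and effects. On those assumptions the choice of rule changes the P<0.05 verdict in roughly 1-6% of runs at 0.46 SD and almost never at 1.0 SD, with little change in average bias. This does not show that the result will be biased. The primary covariate set is open to argument after the data are seen, and that is cheap to prevent.

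**What to change.** Replace the two AIC sentences in 15.1 with:

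> The primary model contains baseline SCr and the confounders retained by the 10% rule, and no other covariates. AIC (lowest signed value, maximum likelihood, same observations) is used only to choose the correlation structure for that model.

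The same-observations condition matters because AIC is a sum over the data. In one simulated example with AIC near 1830 for 200 subjects, each subject contributes about 1830/200 = 9 points, so losing one to a missing value would swamp the differences being compared.

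The cost is two sentences and no new data. The interval becomes slightly wider when a weak confounder is kept: at 0.46 SD the standard error was a median 2-3% larger in runs where AIC would have dropped one. Overall accuracy was similar under the two rules (root mean squared error 0.164-0.198 for the 10% rule, 0.168-0.197 for AIC). The reason to let the 10% rule decide is therefore its fit with a historical-control comparison, not a gain in precision. Listing the candidate confounders in advance would close the freedom that remains, but is a separate step.

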15.2 Secondary Analyses

A number of secondary outcomes will be examined for the study cohort. These outcomes include the incidence of dialysis, mortality, and liver transplantation at day 30 and 90. The

incidence of kidney transplant within one year of liver transplant will also be determined. Additionally, descriptive comparisons of SCr will be undertaken at day 30 and 90 of follow up and at 4 time points after receipt of liver transplantation (day 30, 90, 180 and 365) and also at similar time points for those patients who were transplant ineligible or did not undergo a transplant. Incidence will be calculated as the number of new events during the observation period divided by the total persons at risk. All statistical analyses will be conducted using Stata version 15.1 statistical software (StataCorp, College Park, TX). Statistical significance will be declared for a two-sided hypothesis test if the *P* value was <0.05.

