7.2 Number of Subjects to be Studied

Prospective Terlipressin Group - approximately 50 Terlipressin treated subjects. Retrospective Control Group - approximately 15-25 subjects per clinical site that were treated for HRS-AKI according to center's standard-of-care (Midodrine/Octreotide (M&O), albumin, or other vasopressor) that would have met the inclusion/exclusion criteria below as well as having critical clinical data points to enable a comparison of the Prospective and Retrospective groups. Retrospective cases collected from each site should include eligible patients starting from prior to site IRB approval for this protocol and going back to January 2015. Subjects enrolled in a blinded clinical trial in this time period are excluded.

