13.2 Secondary Efficacy Variables

- Improvement of renal function (SCr) from Day 1 through end of treatment, repeated measure analysis as compared to the Retrospective Control Group.
- For the Prospective Terlipressin Group alone and also in comparison to the Retrospective Control Group:
 - Incidence of dialysis by Day 30 and Day 90 of follow up.
 - Survival by Day 30 and Day 90 follow up.
 - Transplant by Day 30 and Day 90 follow up.
 - Serum creatinine at Day 30 and Day 90 follow up
 - Serum creatinine and incidence of dialysis at Day 30, Day 90, Day 180, and Day 365 after liver transplantation
 - Incidence of kidney transplant within one year after liver transplant
 - Descriptive analysis of number simultaneous liver kidney transplants and episodes of graft rejection at Day 90 and Day 365 after liver transplant

14 Serious Adverse Events

Only Serious Adverse Events will be collected for this study for the prospective group only. Safety review and assessments will be made only for the Prospective Terlipressin Group from time of first dose through 30 days after end of treatment. SAEs are collected from the start of study drug until 30 days after study drug was discontinued. Non-serious Adverse Events are not required to be collected for this study.

The investigator will record the nature, causality, severity, treatment, and outcome of the SAE, and will determine whether there is a “reasonable probability” that the study drug treatment caused the event.

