unexpected, and there is evidence suggesting a causal relationship between the study drug and the event (e.g., death from anaphylaxis).

The sponsor will notify all participating Investigators of safety reports, in a blinded fashion, of potential serious risks as described in the safety review plan for this study.

15 Statistical Plan

Baseline characteristics, such as patient demographics, disease etiology, disease severity and factors present at time of listing for liver transplantation, will be compared between the terlipressin treatment group and the retrospective control group. Categorical variables will be presented as proportions and percentages and compared using chi-squared or Fisher's exact testing. Continuous variables will be presented as means and standard deviations or medians and interquartile ranges. Depending on the distribution of the variable, the Student's t-test or Wilcoxon rank sum will be used for comparison.

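### Day 30/90 dialysis, survival and transplant are compared with non-randomised historical controls under a P<0.05 rule, but no confounder adjustment is specified for them

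*Combined protocol and SAP*

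**What the plan says.** The comparator is a chart-review group from the participating sites, with 2015 as the earliest year: "Retrospective cases collected from each site should include eligible patients starting from prior to site IRB approval for this protocol and going back to January" (Section 7.2). Section 13.2, like Section 5.1 and the synopsis, lists dialysis, survival and transplant by Day 30 and Day 90 "For the Prospective Terlipressin Group alone and also in comparison to the Retrospective Control Group".

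Section 15.2 takes up the same three outcomes ("These outcomes include the incidence of dialysis, mortality, and liver transplantation at day 30 and 90") and gives one estimator for them: "Incidence will be calculated as the number of new events during the observation period divided by the total persons at risk". It then adds a general rule, "Statistical significance will be declared for a two-sided hypothesis test", at P below 0.05. It names no test, regression model, covariate, matching, weighting or stratification for these outcomes.

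Section 15.1 does deal with confounding, but for SCr. There, "All potential confounders will be added to the model and sequentially removed if they do not confound the association", and a confounder stays in if it produces at least a 10% "change in the coefficient for the association between terlipressin and improvement in SCr will be retained in the final model". The only between-group test named for binary data is in the opening paragraph of Section 15, on baseline characteristics: "Categorical variables will be presented as proportions and percentages and compared using chi-squared or Fisher's exact testing".

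**The concern.** The plan accepts that the terlipressin-versus-control contrast is confounded when the outcome is SCr. It then leaves the same contrast without protection when the outcome is death, dialysis or transplant. The 15.1 retention rule cannot be carried over as written, because it is defined by the change in the SCr coefficient.

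Two features of the design make baseline differences plausible. Up to 25 of about 50 prospective patients may be transplant-ineligible (Section 7.3), with no corresponding share set for controls, and eligibility largely decides who can be transplanted. Controls must also have had at least 48 hours of treatment (Sections 6.1 and 8.4), and no such minimum is stated for terlipressin patients.

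If an analyst applies the crude tests that the plan names elsewhere, a difference in case mix could be reported as a significant difference in survival or dialysis, or could cancel a real one. If the analyst adjusts, the covariates would be chosen after the data are seen.

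**Working it through.** **The plan's own figures.** There are none for dialysis, mortality or transplant. The only computed figures are the detectable SCr differences in 15.3, for 50 versus 150 patients. The formula is (1.96 + 0.84) × SD × √(1/50 + 1/150). At SD 1.00 it gives 0.458, against 0.46 in the plan. The columns for SD 0.75, 0.50 and 0.10 also reproduce. The SD 0.20 column does not (0.091 against 0.11), but that has no bearing here. The group sizes of 50 and 150 are used below.

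**Inputs not in the documents.** All event risks, prevalences and severity differences below are assumptions. In every setting the drug has no effect, so every rejection is false.

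**Rejection probability of a crude two-sided test.** With true risks p1 (n = 50) and p2 (n = 150) and pooled risk p:
- SE0 = √[p(1−p)(1/50 + 1/150)] and SE1 = √[p1(1−p1)/50 + p2(1−p2)/150]
- with d = p1 − p2, P(reject) = 1 − Φ((1.96·SE0 − d)/SE1) + Φ((−1.96·SE0 − d)/SE1)

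**Illustration A: terlipressin patients less severe.** MELD has SD 5 and is lower in the terlipressin group. Mortality is logistic in MELD, with the intercept set to give the control mortality shown, and p1 is the logistic risk averaged over the shifted MELD distribution.

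| MELD shift, OR per point | Control 50%: p1 | Formula | Simulation | Control 25%: p1 | Formula | Simulation |
|---|---|---|---|---|---|---|
| 2 points, 1.06 | 47% | 6% | 7% | 23% | 6% | 6% |
| 3 points, 1.10 | 43% | 13% | 14% | 20% | 10% | 9% |
| 5 points, 1.15 | 35% | 47% | 49% | 15% | 30% | 32% |

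Strongest case at 50%: p1 = 0.347, p = (50 × 0.347 + 150 × 0.50)/200 = 0.462, SE0 = 0.0814, SE1 = 0.0787. The rejection probability is Φ((0.153 − 0.160)/0.0787), about 0.47. Formula and simulation differ by the normal approximation and simulation error. At 50% control mortality the picture is symmetric: a shift of the same size the other way gives the same rejection rate against terlipressin.

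**Illustration B: an adverse factor commoner in the terlipressin group.** The factor is present in 50% of that group (25 of 50 is the cap for transplant-ineligible patients).
- Present in 20% of controls: crude rejection is 12% (risk 30% without and 50% with the factor), 21% (30%, 60%) or 36% (20%, 60%). For the middle case, p1 = 0.30 + 0.30 × 0.5 = 0.45 and p2 = 0.30 + 0.30 × 0.2 = 0.36.
- Present in 10% of controls: 18%, 34% and 58%.
- Equal prevalence: 5%.
- Transplant outcome, if only eligible patients can be transplanted (30-50% of them) and the eligible share is 50% versus 75%: 19-36%.

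**What adjustment does.** In 2,000 simulated trials per setting, logistic regression including the factor rejected 4.9% of the time against 19.8% crude (30%/60%, prevalence 50% versus 20%). It rejected 5.7% against 32.4% (30%/60%, 50% versus 10%), and 4.8% against 37.6% (20%/60%, 50% versus 20%).

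**How many covariates the data can carry.** At 25-50% mortality, 200 patients give 50-100 deaths. With a working rule of 10 events per parameter, that allows 5-10 parameters. Treatment, eligibility group, MELD and age use 4. A model with five covariates, treatment, and indicators for 5-10 sites needs 5 + 1 + 4 = 10 to 5 + 1 + 9 = 15, which is too many at 50 deaths.

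**The case against.** The strongest reply is that the plan is silent rather than wrong. A reader might infer that 15.2 prescribes unadjusted tests. It does not: chi-squared and Fisher tests are named only for baseline characteristics, 15.2 speaks of the study cohort, and the P<0.05 sentence follows the software statement and reads as a general convention. That stands, and the point is therefore that no adjustment is specified.

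The synopsis also calls the efficacy and safety analysis descriptive, and 15.3 describes these outcomes as being explored and likely underpowered. This softens the point but does not remove it. Within 15.2 the word descriptive is attached only to the follow-up SCr comparisons, the significance rule has no exemption, and low power gives no protection against bias.

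A reader might also infer that terlipressin will look falsely better. The documents do not support a direction. Controls must meet the same entry criteria, including the MELD and ACLF limits, and come from the same sites, which limits imbalance. The transplant-ineligible allowance and the 48-hour condition could work against terlipressin. A 5-point MELD shift is a full assumed SD and marks the extreme. Nor do the documents show that these outcomes depend more strongly on baseline severity than SCr does; the point does not need that.

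Finally, adjustment has limits. Section 7.2 asks only for undefined critical data points in controls, so covariate availability is not assured; alcoholic hepatitis, for instance, appears only as an exception to an exclusion criterion, not as a named data field. MELD contains SCr, so the two overlap.

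**Conclusion.** The point holds in this form: outcomes that readers will take as clinical benefit are compared with historical controls under a significance rule, and the plan specifies no control of confounding for them although it does for SCr. Following the text as it stands yields crude comparisons whose false-positive rate can range from barely above nominal to close to one half under the assumed MELD differences. The rates depend wholly on assumed imbalance and event risks, and show what could happen rather than what will. These are secondary outcomes, so the change is advisable rather than critical to the trial.

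**What to change.** Add to 15.2:

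- A pre-specified adjusted comparison (logistic or Cox) of Day 30/90 dialysis, survival and transplant, with a small fixed covariate set available in both groups: transplant-eligibility group, baseline MELD and age. Alternatively, use a single propensity score that also includes enrollment SCr and site.
- Site handled by stratification or a random effect, not by indicators; Firth penalisation where events are sparse.
- Crude rates shown beside the adjusted results.
- Any P<0.05 statement for these outcomes based on the adjusted result only. If no adjusted analysis is adopted, report the comparisons as descriptive with confidence intervals and no significance claim, and reconcile the synopsis with 15.2 accordingly.
- The chosen covariates named in 7.2 among the data points required of control cases.

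The cost is extra analysis, a check that the covariates exist in control charts, and somewhat wider intervals. Adjustment will not remove bias from unmeasured factors or from the 48-hour treatment condition for controls. The latter needs an aligned starting point or a landmark analysis, and should be stated as a limitation if left as it is.
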